#### **5.3.2 Exclusion Criteria**

Individuals not eligible to be enrolled into this protocol are those who:

- 1. Are pregnant or nursing, or are women of child bearing potential who are not practicing an effective means of birth control;
- 2. Have a history of, or a current primary psychotic disorder, bipolar affective disorder type 1 or, dissociative identity disorder;
- 3. Have evidence or history of coronary artery disease or cerebral or peripheral vascular disease, hepatic disease with abnormal liver enzymes, or any other medical disorder judged by the investigator to significantly increase the risk of MDMA administration;
- 4. Have hypertension using the standard criteria of the American Heart Association (values of 140/90 or higher assessed on three separate occasions [77]), unless their hypertension has been successfully treated and is currently well-controlled on antihypertensive medicines, In this case subjects with well-controlled hypertension may be enrolled if they pass additional screening to rule out underlying cardiovascular disease (see "Methods");
- 5. Have liver disease with the exception of asymptomatic subjects with Hepatitis C who have undergone additional evaluation (see "Methods"). Subjects with Hepatitis C may be enrolled if they have received appropriate screening (see "Methods");
- 6. Have history of hyponatremia or hyperthermia;
- 7. Weigh less than 48 kg;
- 8. Would present a serious suicide risk, as determined through psychiatric interview, responses to C-SSRS and through the clinical judgment of the investigator, or who, in the judgment of the investigator, are likely to require hospitalization during the course of the study;

- 9. Would present a serious risk to others as established through clinical interview and contact with treating psychiatrist;
- 10. Have used "Ecstasy" (material represented as containing MDMA) more than five times within the last 10 years or at least once within 6 months of the MDMA session;
- 11. Require ongoing concomitant therapy with a psychotropic drug;
- 12. Meet Diagnostic and Statistical Manual of Mental Disorders (DSM)-IV criteria for active substance abuse or dependence for any substance save caffeine or nicotine in the past 60 days;
- 13. Are not able to give adequate informed consent;
- 14. Have any current problem or a history of substance abuse which, in the opinion of the investigator or medical monitor, might interfere with participation in the protocol.

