## **5.0 Randomization and Blinding**

This is a randomized, triple-blind, dose response study with an open-label cross-over segment. For Stage 1, a randomization list will be prepared at the beginning of the study. If needed, subsequent randomization lists will be created to replace subjects who withdraw from the study to ensure that replacement subjects are not added to the end of the initial list. Each subject will be assigned to one of the three dose conditions; 30 mg (low dose), 75 mg (medium dose) or 125 mg (full dose). Twelve evaluable subjects will be assigned to the full dose condition, six evaluable subjects to the 75 mg condition and six evaluable subjects to the 30 mg low dose condition. The study will employ a blinded randomization procedure that will maintain the 2:1:1 ratio while maintaining the blind and ensuring that each subsequent condition assignment is not predicated on the previous assignment.

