## **8.0 Analyses**

In general, nominal variables will be described in terms of frequencies and percentages and analyzed using chi square analysis. Ordinal and non-normal continuous variables will be described using sample median and range, and analyzed by non-parametric statistical tests, and approximately normal variables will be described using sample mean and standard deviations and analyzed by parametric statistical tests. All statistical tests will be two-sided and a difference resulting in a p-value of less than or equal to 0.05 will be considered statistically significant. All p-values will be rounded to and displayed in four decimals. If a p-value less than 0.0001 occurs it will be shown in tables as <0.0001.

Clinical data will be presented in tabular format. Data not subject to analysis according to this plan will not appear in any tables or graphs, but will be included in the data listings.

Analyses will be carried out with SAS Version 9.3 or higher. Selected results may be presented graphically using standard graphical software.

Post-hoc exploratory analyses not identified in this SAP may be performed to further examine the study data. These analyses will be clearly identified as such in the final clinical study report.

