### Columbia Suicide Severity Rating Scale (C-SSRS)

Suicidal ideation and behavior will be summarized according to suggestions made in the Columbia-Suicide Severity Rating Scale Scoring and Data Analysis Guide [3]. A positive response for suicidal ideation is counted when a subject answers "yes" to any one of the five suicidal ideation questions (Categories 1-5) on the C-SSRS, i.e. a score > 0 for suicidal ideation score. Serious suicidal ideation is a suicidal ideation score of 4 or 5. A positive response for suicidal behavior occurs when a subject answers "yes" to any one of the five suicidal behavior questions (Categories 6-10) on the C-SSRS, i.e. a score > 0 for suicidal behavior score. The number and percent of positive responses of Positive Ideation, Serious Ideation, and Positive Behavior will be tabulated by treatment group and time period. P-values will be calculated using the chi-squared test for overall treatment group differences and Fisher's exact test will be used for pairwise testing. Compare lifetime serious suicidal ideation and positive behavior frequencies to cumulative frequencies anytime during the study until end of stage 1 and stage 2 using chi-squared test for overall treatment group differences and Fisher's exact test for pairwise testing.

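### The overall C-SSRS comparison uses an asymptotic chi-squared test on arms of about 12/6/6, so its p-value is unreliable in certain sparse tables, although overall type I error is not inflated

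*SAP*

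**What the plan says.** SAP 8.9.4, in the paragraph on the C-SSRS, defines three yes/no outcomes and says that "The number and percent of positive responses of Positive Ideation, Serious Ideation, and Positive Behavior will be tabulated by treatment group and time period". For these, "P-values will be calculated using the chi-squared test for overall treatment group differences", while "Fisher's exact test will be used for pairwise testing". The comparison of lifetime with on-study frequencies repeats the combination, "using chi-squared test for overall treatment group differences and Fisher's exact test for pairwise testing".

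SAP 8.0 sets the general rule that "nominal variables will be described in terms of frequencies and percentages and analyzed using chi square analysis". It also sets the threshold: "All statistical tests will be two-sided and a difference resulting in a p-value of less than or equal to 0.05" counts as significant, and p-values are shown to four decimals. SAP 5.0 gives the arm sizes: "Twelve evaluable subjects will be assigned to the full dose condition, six evaluable subjects to the 75 mg condition and six evaluable subjects". The second group of six receives the 30 mg dose.

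Neither document has a rule that moves the overall test to an exact method when counts are small. Neither gives an expected C-SSRS event rate.

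**The concern.** The chi-squared p-value is a large-sample approximation, and two of the three arms have six subjects. The SAP already uses an exact method for pairs of arms, but keeps the approximation for the overall test on the same counts. A significant overall p-value for suicidality could then be printed beside three non-significant pairwise tests, with no exact overall test to support it.

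Comparing suicidality between conditions is a stated safety objective (Protocol 3.3, SAP 3.3). The overall test is repeated over three outcomes and several time periods, so one such table could attract attention that the data do not warrant.

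**Working it through.** The plan states no power, event rate or p-value for the C-SSRS, so there is no figure of its own to reproduce.

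**Inputs**
- Arms of 12/6/6, written full/medium/low, N = 24 (SAP 5.0).
- Significance at p ≤ 0.05, two-sided (SAP 8.0).
- Chi-squared test with 2 df overall, Fisher's exact test for pairs (SAP 8.9.4).
- Event rate: an assumption, tried from 2% to 50%. Low counts of serious ideation or behaviour are plausible because Protocol 5.3.2 excludes anyone who "Would present a serious suicide risk, as determined through psychiatric interview". This is less sure for any ideation.

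**Expected counts.** With k events in total, a six-subject arm expects 6k/24 = k/4 events and 6 − k/4 non-events. These sum to 6, so both cannot reach 5. The same is true of any arm with fewer than 10 subjects, so a few replacement subjects do not change it.

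**Table 0/0/2 (k = 2).**
- Expected events are 1, 0.5 and 0.5; expected non-events are 11, 5.5 and 5.5.
- X² = (1/1 + 1/11) + (0.25/0.5 + 0.25/5.5) + (2.25/0.5 + 2.25/5.5) = 6.545. With 2 df, p = exp(−6.545/2) = 0.0379.
- Exact: the probability of this table is C(6,2)/C(24,2) = 15/276. The only other table as improbable is 0/2/0. So p = 30/276 = 0.1087.
- Pairwise Fisher: 0/12 v 2/6 gives C(6,2)/C(18,2) = 15/153 = 0.098. 0/6 v 2/6 gives 0.4545. 0/12 v 0/6 gives 1.

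**Table 1/0/3 (k = 4).**
- Expected events are 2, 1 and 1; expected non-events are 10, 5 and 5.
- X² = (1/2 + 1/10) + (1/1 + 1/5) + (4/1 + 4/5) = 6.6, so p = exp(−3.3) = 0.0369.
- Exact: the tables no more probable than this one have weights 15 + 15 + 120 + 120 + 225 + 240 + 240 = 975 out of C(24,4) = 10,626. So p = 0.0918.
- The smallest pairwise Fisher p is 0.0833.

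**Null rejection rate given the event total**

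| Events | Chi-squared | Exact |
|---|---|---|
| 1 | 0 | 0 |
| 2 | 10.9% | 0 |
| 3 | 2.0% | 2.0% |
| 4 | 7.1% | 4.7% |
| 5 | 4.6% | 4.6% |

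**Size averaged over event totals**

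| Common event rate | Chi-squared | Exact |
|---|---|---|
| 2% | 0.8% | 0.03% |
| 5% | 2.8% | 0.3% |
| 10% | 4.7% | 1.4% |
| 20% | 5.1% | 3.6% |

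The chi-squared maximum over rates up to 50% is about 5.2%. As a check at 5%: P(2 events) = 276 × 0.05² × 0.95²² = 0.223, which contributes 0.223 × 0.1087 = 0.0243. Totals of 3, 4 and 5 add about 0.0017, 0.0017 and 0.0002. The sum is 0.028.

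**How often the tests disagree.** Of the 637 possible tables, 328 have chi-squared p ≤ 0.05. In 22 of those the exact overall p exceeds 0.05, running from 0.058 to 0.109. In 18 of the 22 no pairwise Fisher test reaches 0.05 either. With three events in one six-subject arm (0/0/3) both tests reject: 0.0058 and 0.0198.

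**The case against.** The case for leaving the SAP alone is substantial.

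- **No alpha inflation.** A reader might infer that the test raises the false-positive rate generally. It does not: averaged over event totals its size is at or near nominal, and below it when events are rare. The 10.9% applies only once two events have occurred.
- **The discordant tables are not the usual ones.** A reader might take 0/0/2 as the table to expect. The documents give no rate, and even with exactly two events, the chance that both fall in the same six-subject arm is 10.9% under the null. The probability of chi-squared p ≤ 0.05 with exact p > 0.05 is 0.8%, 2.5%, 3.5% and 1.9% at rates of 2%, 5%, 10% and 20%.
- **The exact values are not remote.** A reader might also infer that the exact results are far from significant. In the discordant tables they lie between 0.058 and 0.109.
- **The exact test has its own cost.** Its size is 0.3% at a 5% rate and 1.4% at 10%, which is more than slight conservatism. For a suicidality screen, a less conservative test can be defended.
- **It does not remove every disagreement with the pairs.** For 0/2/2 the exact overall p is 495/10,626 = 0.047 while the pairwise values are 0.098, 0.098 and 1; chi-squared gives 0.091. The exact overall test is significant with no significant pair in 20 of 637 tables, against 36 for chi-squared.
- **The example depends on the arm sizes.** The safety population is everyone treated and dropouts are replaced, so arms may differ from 12/6/6. Both events in the arm of seven at 12/6/7 give chi-squared p = 0.061, and 12/7/7 gives 0.053. At 12/7/6 with both events in the arm of six, the exact p is 15/300 = 0.05, which the SAP would itself call significant. At 13/6/6 and 14/7/7 the discrepancy remains (0.032 v 0.100 and 0.0395 v 0.111).
- **Little depends on the p-value.** Adverse-event reporting is the primary safety measure, the trial is an unpowered pilot, and the counts are tabulated anyway.

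All of this stands as a limit on the size of the point. It does not make the printed p-value dependable in the sparse tables where it departs from the exact one. Nor does it explain why the overall test is approximate when the pairwise tests are exact.

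**Conclusion.** The point holds in a limited form. The SAP specifies an approximate overall test where the usual expected-count condition can never be met. In particular sparse tables the result can be a significant overall suicidality p-value that neither an exact overall test nor any pairwise test supports. In the clearest case, 0/0/2, the printed p is too small by a factor of 0.1087/0.0379 = 2.9.

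The harm is confined to individual tables, mainly those with two events, or three of four, in one six-subject arm. The figures assume arms of 12/6/6; the averaged sizes also assume a common event rate. Severity is the lowest: a cheap improvement to a supporting safety analysis.

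**What to change.** In SAP 8.9.4, in both C-SSRS comparisons, replace the chi-squared test for overall group differences with the Fisher-Freeman-Halton exact test. Keep Fisher's exact test for pairs, and print the count and denominator for each arm beside every p-value. In SAP 8.0, add that nominal tables with any expected count below 5 are analysed by an exact test. With six-subject arms, this covers every three-arm nominal table.

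The cost is one option in the SAS procedure already planned, with no effect on conduct, data collection or sample size. The SAP should acknowledge the trade-off: with rare events the exact test will seldom reject, so a non-significant result is not evidence of no difference and the tabulated counts carry the information. It should also say that the overall and pairwise results can still occasionally differ.

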#### 5.1 Planned Duration of Protocol

Stage 1 will take up to six months (full dose group) or four months (medium and low dose groups) to complete after screening and baseline evaluation. The screening and baseline evaluation can take up to 4 months. In addition, if the length of time between the end of tapering and the first experimental session is longer than a month, the CAPS should be repeated to show consistency between this score and the baseline CAPS. The open-label study segment for participants initially assigned to receive low dose or medium-dose MDMA (Stage 2) will last an additional five months from the single introductory and review psychotherapy session until the evaluation two months after the final open-label MDMA-assisted psychotherapy session. The time period between the end of Stage 1 and the start of Stage 2 should not exceed 5 months for any participant with CAPS re-assessment done if there is an interval of greater than 8 weeks between the end of Stage 1 and the beginning of Stage 2. The 12-month follow-up will occur a year after the final experimental session for all participants who complete Stage 1 only, and a year after the final open-label session for any participants who enroll in and complete

Stage 2. For each participant who enrolls only in Stage 1, the entire study duration will be up to 1.5 years including the 12-month long-term follow-up, and for the participants that complete both Stage 1 and Stage 2 follow-ups, the study may take about two years.

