The C-SSRS is a clinician-administered measure of suicidal behavior devised to detect potential suicidal thoughts or behaviors during a clinical trial [91]. It consists of a "Baseline" form that assesses lifetime suicidal ideation, ideation intensity and behavior, and a form for assessing current suicidal ideation, and intensity. The C-SSRS consists of a series of questions, and can be administered during face-to-face interview or over the telephone. The C-SSRS will be administered by the investigators in accordance with the Time and Events table. The measure will be administered at baseline, during the second

preparatory session, twice during experimental sessions (once before and once after drug administration), on two days of telephone contact, during each integrative psychotherapy session and at the evaluation at the end of Stage 1, end of Stage 2 and the 12-month follow-up. Participants undergoing medication washout will complete the C-SSRS before and after medication washout.

A 100-millimeter visual analog scale will be used to assess changes in symptoms of preexisting tinnitus and/or chronic pain [92-94]. The Changes in Tinnitus and/or Pain visual analog scale will allow rating of symptom severity from "None" to "Worst Case Imaginable". This exploratory measure will enable quantification of subjective somatic symptoms that are known to be associated with PTSD [93, 95-97]. Presence of chronic pain is associated with PTSD, possibly as a result of psychological response to traumatic stress as reflected in brain activity, such as increased amygdalar activity in response to pain and transmitter systems involved in the stress response [93, 96, 97].

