### 8.5 Baseline Values

Baseline values are from screening/baseline visit for all measures, except C-SSRS. For C-SSRS, pre-enrollment scores will be used as a measure of ‘lifetime’ suicidal ideation and behavior, and preparatory session 2 (visit 3) pre-drug Since Last Visit C-SSRS scores will be used as ‘baseline.’ If a subject was not administered the C-SSRS at preparatory session 2 (visit 3), then ‘baseline’ scores will be from preparatory session 3 (visit 4).

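### SAP 8.9.4 sets lifetime suicidality against on-study suicidality with no allowance for unequal look-back or for pairing, so the contrast cannot be read as a change in risk

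*SAP*

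**What the plan says.** The C-SSRS paragraph of SAP 8.9.4 contains two analyses.

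- Positive ideation, serious ideation and positive behavior "will be tabulated by treatment group and time period", with a chi-squared test across groups and Fisher's exact test for pairs of groups.
- A further instruction to "Compare lifetime serious suicidal ideation and positive behavior frequencies to cumulative frequencies anytime during the study until end of stage 1 and stage 2", again "using chi-squared test for overall treatment group differences" and Fisher's exact test for pairs.

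The two sides of the second analysis come from different look-backs. SAP 8.5 states that "pre-enrollment scores will be used as a measure of" lifetime ideation and behavior, and Protocol 6.1.2 describes a baseline form that "assesses lifetime suicidal ideation, ideation intensity and behavior". The on-study side accumulates any positive response up to each cut-off. SAP 8.5 also defines a separate pre-drug reference: "preparatory session 2 (visit 3) pre-drug Since Last Visit C-SSRS scores will be used as" baseline, with Visit 4 as the substitute if Visit 3 is missing. The lifetime comparison does not use it.

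Protocol 5.1 puts Stage 1 at up to six months for the full dose group and four months for the other two. Stage 2 adds five months, after a gap of no more than five months. Protocol 5.3.2 excludes a person who "Would present a serious suicide risk, as determined through psychiatric interview, responses to C-SSRS" and clinical judgment. A past history alone does not exclude.

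**The concern.** A proportion ever positive grows with the time over which subjects could have become positive. Here one proportion covers a whole life in people aged at least 18, and the other covers months. The plan gives no equal look-back, rate or within-subject table. Entry screening for serious suicide risk lowers the on-study proportion further.

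Protocol 7.3 says that stopping PTSD medication and the effects of MDMA-assisted psychotherapy may raise the likelihood of suicidal ideation or behavior, and suicidality is a named safety objective in both documents. A table in which the proportion drops from lifetime to on-study invites the reading that treatment lowered risk, when the drop may only reflect the shorter window. The attached tests do not settle it. As worded they compare arms, and if applied to lifetime against on-study they would treat paired observations as independent samples.

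**Working it through.** **1. On-study windows.** The upper visit windows in the Stage 1 Time and Events table reproduce the stated durations (1 month = 4.35 weeks):

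- Low and medium dose, V1 to V13: 7 weeks + 5 weeks + 1 month = 16.3 weeks = 3.8 months (stated: up to 4).
- Full dose, V1 to V18: 7 + 5 + 5 weeks + 2 months = 25.7 weeks = 5.9 months (stated: up to 6).
- Crossover subjects to end of Stage 2: 4 + 0 + 5 = 9 months to 4 + 5 + 5 = 14 months.

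**2. Break-even.** Let p be lifetime prevalence, T the years over which that risk accrued, t the months on study and k the multiple by which the hazard changes on study. Under a constant hazard the expected on-study frequency is

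q = 1 − (1 − p)^(k·t/(12T)).

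Setting q = p gives k = 12T/t, whatever p is. That is the rise in hazard needed before the on-study frequency even equals the lifetime one.

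| Look-back T | t = 4 | t = 6 | t = 14 |
|---|---|---|---|
| 18 years (minimum age) | 54 | 36 | 15.4 |
| 10 years | 30 | 20 | 8.6 |
| 5 years | 15 | 10 | 4.3 |
| 1 year | 3 | 2 | 0.9 |
| 0.5 year (minimum PTSD duration) | 1.5 | 1 | 0.4 |

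**3. Expected frequencies.** The documents give neither p nor T. With p assumed to be 40%:

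| T | 6 months, k = 1 | 6 months, k = 5 | 14 months, k = 1 | 14 months, k = 5 |
|---|---|---|---|---|
| 20 years | 1.3% | 6.2% | 2.9% | 13.8% |
| 10 years | 2.5% | 12.0% | 5.8% | 25.8% |
| 5 years | 5.0% | 22.5% | 11.2% | 44.9% |
| 1 year | 22.5% | 72.1% | 44.9% | 94.9% |

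Entries below 40% read as a fall. With p = 50% and T = 18 years, no change gives 1.3% at 4 months and 1.9% at 6 months; a five-fold rise gives 6.2% and 9.2%. With p = 50%, T = 5 years, k = 5 and t = 14 months, q = 1 − 0.5^(70/60) = 55%, which is above 50%.

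**4. Chance of an observed fall.** Full-dose arm, n = 12, 6 months, p = 40%, five-fold rise, the two counts treated as independent binomials: 97% for T = 20 years, 92% for 10, 76% for 5 and 3% for 1. The real counts are paired, so these figures are indicative.

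**5. Pairing, without a hazard model.** Let b be the subjects with a history who are not positive on study, and c those positive on study with no history. Subjects positive in both periods cancel, so on-study frequency exceeds lifetime frequency only if c > b. Take assumed counts for 12 subjects: 6 have a history, 2 of them recur, and 3 of the 6 without a history become positive. The margins read 6/12 against 2 + 3 = 5/12, a fall, although half of those without a history had a first event on study. The margins hide c; a 2×2 table shows it.

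**The case against.** The strongest reply is that the tests are for differences between arms, in line with the safety objective of comparing conditions. All arms share the lifetime look-back, so its length creates no false fall in an arm contrast. That stands as a reading of the tests, but it leaves the instructed lifetime-to-study comparison with no method of its own. The SAP does not say whether that contrast is tested or only displayed.

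A reader might infer that a fall is built in, whatever the truth. The documents do not support that. Prevalence and constant hazard are assumptions. At least 18 of the 24 subjects must have PTSD of under 10 years' duration, so risk may be concentrated in recent years. Repeated C-SSRS administration raises on-study detection, against the effect of the entry exclusion. At a 1-year look-back, or at 5 years with a five-fold rise and a 14-month window, the on-study frequency can exceed the lifetime one.

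A reader might also infer that the trial would miss a rise in suicidality. That does not follow either. The by-group, by-period C-SSRS tables, serious adverse events by group and psychiatric-status adverse events all remain and could show it, although 12, 6 and 6 subjects give little power.

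The SAP cites an external C-SSRS scoring guide. What it says about this comparison cannot be checked here.

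**Conclusion.** The point holds for this one comparison. It contrasts proportions over very different windows, ignores the pairing, and carries tests that answer a different question. At the Stage 1 cut-off, with look-backs of about 5 years or more and a constant hazard, a fall is expected with no change in risk, and a five-fold rise would usually still read as a fall (76% to 97% of the time in the full-dose arm under the assumptions above). The size depends on two quantities the documents do not give: lifetime prevalence and when that risk accrued. The mismatch is smaller at the end of Stage 2, and it shrinks or reverses where risk is recent. The defect is worth correcting before analysis, but it does not undermine the rest of the suicidality reporting.

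**What to change.** In SAP 8.9.4, remove the comparison of lifetime with on-study frequency as a before/after contrast, whether tested or displayed.

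- Use lifetime status as descriptive history. For each arm and each cut-off, cross-tabulate lifetime (yes/no) by on-study (yes/no), separately for serious ideation and positive behavior. Report the subjects positive on study with no lifetime history.
- For change from the pre-drug state, show within-subject shifts from the Visit 3 (or Visit 4) baseline already defined in SAP 8.5, and state the look-back length of each period.
- State which hypothesis any remaining chi-squared or Fisher test addresses.

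Positive subjects per subject-month would be a poor substitute. Each subject counts once however long the window, so at a constant hazard longer windows give lower values.

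The cost is SAP wording and a changed table, with no new data. The drawback is that the Visit 3 look-back is short and may overlap medication washout, so that baseline is imprecise and may already carry some effect of stopping medication.
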